NCT number: Not yet assigned

Protocol ID PI20/1645

Date: December 21, 2021

FGF23 and cardiovascular damage in anemia with or without chronic kidney disease.

CONFIDENTIALITY DECLARATION

The information contained in this document is the property of the promoter and therefore, it is provided confidentially. It may not be disclosed to other people without the sponsor's written authorization, except for the use that may be made of it to obtain the informed consent of the people who are to receive the investigational drug, as well as in communications to the competent health authorities, the Research Ethics Committees or those people who will carry out the study.

GENERAL INFORMATION

A. Identifiers:

- Protocol ID PI20/1645

- Title: **FGF23 and cardiovascular damage in anemia with and without chronic kidney disease.**

B. Treatment group description:

Group 1: Patients with iron deficiency anemia with chronic kidney disease, stages 3, 4 and 5 non on dialysis, treated with oral or intravenous iron for 3 months

Group 2: Patients with iron deficiency anemia with normal renal function, treated with oral or intravenous iron for 3 months

C. Sponsor:

FIBICO (“Fundación para la Investigación Biomédica de Córdoba”)

Hospital Universitario Reina Sofía – Edificio IMIBIC

[name]

[name]

[contact]

Fax: [name]

D. Participants:

Department of Hematology, Internal Medicine and Nephrology of Reina Sofía University Hospital and Maimonides Institute for Biomedical Research of Córdoba (IMIBIC) .

[name]

[name].

PROTOCOL

1. Objectives:

The General Objective of this research project is to evaluate, through in vivo and in vitro studies, the cardiovascular alterations related to the anemia-induced increase in FGF23 production; as well as the identification of possible molecular targets that may be useful in its prevention and / or palliation. This General Objective will be addressed through the following Specific Objectives:

1.- To determine in a population with anemia (due to iron deficiency), with and without chronic kidney disease (CKD), an association between the parameters related to iron metabolism, FGF23 and markers of cardiovascular damage. It will be evaluated:

- 1.1 The levels of FGF23, intact and C-terminal, before and after treatment.

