4.3. Induction of oxidative stress

5.- To evaluate in vitro, in osteoblasts/osteocytes cultures, the direct effect of ferrous sulphate, ferric carboximaltose, ferric citrate and hepcidin on:

5.1. Production of intact FGF23 and C-terminal FGF23.

5.2. Gene and protein expression of intracellular mediators of FGF23 production: DMP1, GALNT3, Phex, FGFR1 and HF1 α .

2. Desing:

2.1: Type: Study in patients: prospective, open, parallel groups.

2.2 Sample size: It is considered that a random sample of 183 individuals for the population of patients with iron deficiency anemia without CKD and 218 for the study to be carried out with patients with anemia and CKD, will be enough to estimate, with a 95% confidence and an accuracy of +/- 5 percentage units, a population percentage that is expected to be around 13% and 15%, respectively. As a percentage of necessary replacements, it is expected to be 5% and 10%, respectively.

3. Study population:

Selection criteria:

This study will include patients who meet all the inclusion criteria and anyone of the exclusion criteria.

Inclusion Criteria:

- Age. 18-85 years old
- Hemoglobin < 11g/dl
- Serum ferritin < 100 ng/ml or transferrin saturation index < 20%
- Written informed consent

Exclusion Criteria:

- Weight < 50 Kg or BMI < 17
- Acute bleeding > 300 ml, within 72 hours before study inclusion
- Proliferative hematologic disease. Hemochromatosis
- Active infections within 30 days before study inclusion
- Systemic inflammatory illness
- HIV, HCV or HBV infection
- Iron active treatment
- Blood transfusion in the last 90 days before inclusion.
- Cardiovascular hospitalization 30 days before study inclusion
- Anticoagulant treatment with coumarinics
- Chronic liver disease
- Immunosupresive therapy
- Erythropoiesis stimulating agents treatment, radiotherapy or quimiotherapy within 30 days before inclusion
- Scheduled major surgery during study period
- Pregnancy or lactation
- Drugs addiction
- Participation in others clinical trials.

Withdrawal criteria:

1. Informed consent withdrawal.
2. Iron treatment intolerance.
3. Medical decision, based on clinical state.

4. Deviation from the protocol, such as intolerance to the treatment or the appearance of new symptoms or pathologies that discourage its continuity.
5. Loss of follow up.

4. Treatment:

Any oral or intravenous iron formulation, prescribed by the responsible clinician. The investigators will not take part in treatment selection.

5. Study procedures:

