The total planned duration of the research project for each patient is 3 months. The outpatients of the nephrology, internal medicine and hematology with the possibility of meeting the requirements will be referred to one of the investigators of the research project who will carry out the following visits and procedures:

V0: After the explanation of the research project and the signing of the informed consent in the first screening visit (V0), the patient's history will be evaluated, anthropometric measurements will be taken, and the existing biochemical data will be studied.

V1: One to two weeks after V0, the patient will be summoned to proceed to take blood samples (one hematimetry tube and 2 biochemistry tubes), collection of the morning urine sample, measurement of hemodynamic parameters, from this moment the patients would begin with the oral or intravenous iron therapy indicated by their responsible doctor.

V2: At month 3 (M3) from the start of the study, blood samples (hematimetry and biochemistry), urine and hemodynamic parameters will be taken. Finishing the study.

Patients who present resistance to oral treatment, maintaining Hb <11 and ferritin <100 ng / ml or TSI <20%, may be transferred to the treatment group with IV iron if so decided by their responsible physicians, V3 will then be programmed.

V3: At month 6 (M6) from the beginning of the study, blood samples (hematimetry and biochemistry), urine and hemodynamic parameters will be taken. Finishing the study.

6. Statistic analysis

Data that follow a Normal distribution will be described as mean \pm standard deviation and non-Normal data will be described as median with interquartile range. The primary end point will be compared between the two treatment groups using an unpaired Student's t-test (possibly after log transformation if the data does not follow a Normal distribution) and as an intention to treat. Changes and differences between groups in secondary end points will be analyzed using paired and unpaired Student's t tests or Wilcoxon and Mann-Whitney tests for continuous variables, and Chi-square or Fisher's exact test for dichotomous variables. Linear mixed models will be used to analyze variables with repeated measures. Linear and logistic regression analyzes with adjustment for various covariates will be applied to the baseline data to investigate any association with the change in various parameters, as well as any association with clinical events.

7. Workplan

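### Section 6 names the pooled-variance Student's t-test for two different patient populations of unequal planned size; Welch's test would be a small and practically free improvement.

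*Protocol*

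**What the plan says.** The protocol defines two groups under its treatment group description: "Group 1: Patients with iron deficiency anemia with chronic kidney disease, stages 3, 4 and 5 non on dialysis", and "Group 2: Patients with iron deficiency anemia with normal renal function, treated with oral or intravenous iron for 3 months". Section 2.2 plans "183 individuals for the population of patients with iron deficiency anemia without CKD and 218 for the study" of patients with CKD.

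For the primary end point, Section 6 states: "The primary end point will be compared between the two treatment groups using an unpaired Student's t-test", with the qualification "possibly after log transformation if the data does not follow a Normal distribution) and as an intention to treat". For continuous secondary end points it lists paired and unpaired Student's tests, with Wilcoxon and Mann-Whitney tests as alternatives. It mentions neither unequal variances nor Welch's version of the test. The log transformation is tied to non-Normality and not to unequal spread.

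The protocol gives no SD for any marker and no significance level for the test, and it does not name the primary end point.

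**The concern.** Student's unpaired test estimates one common variance. In a randomised comparison, equal variance under the null hypothesis is a natural starting point. Here the groups are not randomised samples of one population: one pools three stages of CKD, the other has normal renal function. Markers on the protocol's list such as FGF23, PTH, phosphorus and BNP may well vary more in the CKD group.

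When both the spread and the group sizes differ, the pooled standard error is biased. It is too wide if the more variable group is the larger one, and too narrow if that group is the smaller one. The error rate and the confidence interval of the main contrast would then depend on which group varies more and how recruitment turns out. Both can be avoided by the choice of test.

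**Working it through.** **Inputs from the protocol.** Section 2.2 gives expected percentages of 13% (no CKD) and 15% (CKD), precision of 5 percentage points either way, 95% confidence, replacements of 5% and 10%, and sizes of 183 and 218.

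**Assumptions.** Two-sided 5% test; ratio k of the CKD SD to the non-CKD SD of 1.5, 2 or 3; and the two groups compared are CKD and no CKD.

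**Step 1: reproduce the planned sizes.** n = 1.96² × p(1 − p) / 0.05², then divide by (1 − replacement share).
- No CKD: 173.8; 173.8 / 0.95 = 182.9, so 183.
- CKD: 195.9; 195.9 / 0.90 = 217.7, so 218.

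Both reproduce. The completers implied are 174 and 196.

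**Step 2: pooled against true standard error.** With the non-CKD SD set to 1, in large samples:
- pooled SE² = k²/n(no CKD) + 1/n(CKD)
- true SE² = k²/n(CKD) + 1/n(no CKD)
- R = pooled SE / true SE
- type I error = 2 × [1 − Φ(1.96 R)]
- power, where the correct SE would give 80% = Φ(1.96 + 0.84 − 1.96 R)

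Example, k = 2, 196 versus 174: pooled SE² = 4/174 + 1/196 = 0.02809; true SE² = 4/196 + 1/174 = 0.02616; R = √(0.02809/0.02616) = 1.036. Type I error = 2 × [1 − Φ(2.031)] = 4.2%. Power = Φ(2.80 − 2.03) = 78%.

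**Step 3: results.**

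| CKD vs no CKD | k | R | Type I error | Power |
|---|---|---|---|---|
| 196 vs 174 (planned completers) | 1.5 | 1.023 | 4.5% | 79% |
| | 2 | 1.036 | 4.2% | 78% |
| | 3 | 1.049 | 4.0% | 77% |
| 120 vs 183 (assumed CKD shortfall) | 1.5 | 0.923 | 7.0% | – |
| | 2 | 0.882 | 8.4% | – |
| | 3 | 0.845 | 9.8% | – |

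At the full planned sizes (218 versus 183), the same calculation with the exact t critical value gives 4.2%, 3.8% and 3.5%. If instead the CKD group had half the spread of the other (k = 0.5), type I error would be 5.8% at 196 versus 174 and 6.2% at 218 versus 183.

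**Step 4: simulation with Normal data.** At 196 versus 174 and k = 1.5, 2, 3, Student's test rejected a true null in 4.6%, 4.2% and 4.1% of 40,000 simulated trials; Welch's test did so in 5.1%, 4.9% and 4.9%. In a more extreme assumed case (73 CKD versus 183, k = 2; 100,000 data sets), Student's gave 13.3% and Welch's 5.0%.

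**The case against.** The strongest reply is that nothing harmful happens under the plan as written. At the planned sizes, with CKD the more variable group, the test is slightly conservative and false positives are not inflated. The rates of 7% to 10% need a reversal of the size order that the protocol does not predict. The protocol gives no SD and names no primary end point, so the true ratio is unknown, and the permitted log transformation may shrink a difference in spread that grows with the mean. Equal variance is inferred from the test's name, and an SAP could still specify Welch's version. For secondary end points Student's test is only one option, since rank tests are also named. All of this stands, and it limits the size of the point. It does not remove it: the protocol names the test, and neither the log transformation nor the rank tests are tied to unequal variance in the primary comparison.

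A reader might go further and infer that the mixed models carry a much larger error. Section 6 says "Linear mixed models will be used to analyze variables with repeated measures", and with one common residual variance the before-after change could appear significant too often in CKD and too rarely without it. The protocol does not support this:
- It states no residual structure, a detail commonly left to an SAP.
- Wider spread between CKD patients is absorbed by a random intercept and cancels from the within-patient change. An error would need the SD of the change itself to differ between groups, a separate assumption for which the protocol offers no basis.
- Section 6 already names paired tests for changes in secondary end points; run within a group, these use only that group's variance.

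A reader might also infer that recruitment alone sets the direction of the t-test error. It does not: the direction depends on which group varies more together with which group is larger.

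**Conclusion.** The point holds as a minor one. A pooled-variance test is named for two distinct populations of unequal planned size, where equal spread cannot be taken for granted. For assumed SD ratios of 1.5 to 3 with CKD the more variable, the cost at planned completers is a standard error 2% to 5% too wide and one to three points of power. Inflation to about 7% to 10% requires the more variable group to finish clearly smaller, as in the assumed 120 versus 183.

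These figures rest on assumed SD ratios, a two-sided 5% level, and the reading that the comparison is CKD against no CKD. Section 5 also uses the term treatment group for intravenous iron. If oral against intravenous iron were meant, no group sizes are planned and these figures would not apply, though the advice would be the same. The protocol does not show that the primary test will miss its nominal level by a material amount, and no conclusion about the mixed models is drawn.

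**What to change.** In Section 6, replace the unpaired Student's t-test with Welch's unequal-variance t-test for the primary comparison and for the secondary unpaired t-tests. Apply it on whichever scale is used, original or log, without a preliminary test of variances. Report the confidence interval from the same unequal-variance standard error.

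The cost is a change of wording. Sample size and data collection stay as they are, and at these group sizes Welch's test loses practically nothing if the variances turn out equal. In every scenario simulated its type I error stayed between 4.9% and 5.1%, including those with strongly unbalanced groups.

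### Section 6 fixes the primary comparison as an unadjusted t-test by intention to treat, although the study assigns no treatment and its groups are defined by kidney status

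*Protocol*

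**What the plan says.** Section 6 (Statistic analysis) states how the primary end point is to be compared between what it calls two treatment groups, in these words: "using an unpaired Student's t-test (possibly after log transformation if the data does not follow a Normal distribution) and as an intention to treat". It gives that comparison no covariates and does not name the end point. The same section plans linear mixed models for repeated measures, and regression with unnamed covariates to look for associations with change and with clinical events. Neither is tied to the primary comparison.

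Section B, headed as a description of treatment groups, lists two:
- "Group 1: Patients with iron deficiency anemia with chronic kidney disease", stages 3 to 5 not on dialysis, with three months of iron by either route.
- "Group 2: Patients with iron deficiency anemia with normal renal function, treated with oral or intravenous iron for 3 months".

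Section 2.1 gives the design as "Study in patients: prospective, open, parallel groups", with no mention of randomisation. Section 4 allows any oral or intravenous formulation that the treating clinician prescribes and keeps the investigators out of that choice. Section 5 uses the term treatment group a second time, for intravenous iron, to which patients resistant to oral iron may be moved if their physicians so decide.

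Specific objective 1 is to determine "an association between the parameters related to iron metabolism, FGF23 and markers of cardiovascular damage" in anemic patients with and without CKD.

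**The concern.** Intention to treat means analysing patients by the treatment they were assigned. Its value against confounding comes from random assignment. Here the study assigns nothing, and as section B defines them the groups do not differ in treatment at all. The wording presents an observational contrast as a comparison of assigned treatments.

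The test that goes with the label takes no account of who is in each group. Eligibility is wide: "Age. 18-85 years old", and both sexes by implication, since "Pregnancy or lactation" is an exclusion. Patients are referred from nephrology, internal medicine and hematology, and nothing in the design makes the CKD and non-CKD groups alike. If they differ in age or sex, and the end point depends on either, the t-test takes that difference for a group effect. What is at stake is how the primary result may be interpreted, not whether the data can be used.

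**Working it through.** **1. Which groups, and is anything assigned?**

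| Reading of the two treatment groups | Source | What decides membership |
|---|---|---|
| CKD versus no CKD | Section B | Kidney status at entry |
| Oral versus intravenous iron | Section 5, second use of the term | The clinician (section 4), who may later switch the route |

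Neither reading contains an assignment by the study. Section B points to the first.

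**2. Reproduce the plan's sample size (section 2.2).** The inputs are expected percentages of 13% (no CKD) and 15% (CKD), precision of ±5 points, 95% confidence, and, for losses, "As a percentage of necessary replacements, it is expected to be 5% and 10%, respectively". The formula is n = 1.96² × p(1 − p) / 0.05².
- No CKD: 1.96² × 0.13 × 0.87 / 0.05² = 173.8, so 174; 174 / 0.95 = 183.
- CKD: 1.96² × 0.15 × 0.85 / 0.05² = 195.9, so 196; 196 / 0.90 = 218.

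The stated 183 and 218 reproduce. They give the precision of one percentage per group and were not derived for a t-test.

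**3. What a confounding shift would do (illustration, CKD versus no CKD, continuous end point).** The document gives no SD, no age or sex distribution and no correlations, so the shifts b are assumptions, in SD units.
- SE = √(1/174 + 1/196) = 0.1042 SD.
- Probability of rejection with no CKD effect = Φ(b/SE − 1.96) + Φ(−b/SE − 1.96).

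| Assumed shift b | One way it could arise | 174 vs 196 | 183 vs 218 (SE 0.1003) |
|---|---|---|---|
| 0 | no imbalance | 5.0% | 5.0% |
| 0.05 | age gap 0.5 SD × correlation 0.1, or 20 points more women × 0.25 SD | 7.7% | 7.9% |
| 0.10 | 0.5 SD × 0.2, or 40 points × 0.25 SD | 16% | 17% |
| 0.20 | 1.0 SD × 0.2 | 48% | 51% |

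**4. What adjustment costs in precision.** The share in the CKD group is p = 196/370 and q = 1 − p, so pq = 0.249. The gaps are again assumed.
- Unadjusted, difference detectable with 80% power: 2.802 × 0.1042 = 0.292 SD.
- Age, gap g: variance × (1 + g²pq). For g = 0.5 this is 1.062, giving 0.292 × √1.062 = 0.301 SD. For g = 1.0 it is 1.249, giving 0.326 SD.
- Sex, gap d: variance × 1/(1 − pq d²/0.25), which is 1.04 for 20 points and 1.19 for 40 points.
- Change instead of level: variance × 2(1 − r), where r is the correlation between visits. At r = 0.3 this is 1.4, giving 0.292 × √1.4 = 0.345 SD; at r = 0.7 it is 0.6, a gain.
- Unfavourable combination (r = 0.3, age gap 1.0 SD, sex gap 40 points, age and sex unrelated within groups): 1.4 × (1 + 0.249 + 0.190) = 2.01, giving 0.292 × √2.01 = 0.41 SD.

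**The case against.** **The label has a usable meaning.** Section 3 lists withdrawals for intolerance, deviation and loss to follow-up, and section 5 allows a change of route. The phrase can be read as keeping everyone in the original group despite these. That is fair, and it is the most the phrase can mean. It still gives no protection against confounding.

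**The objective asks only for an association.** This is correct: the protocol does not claim that a group difference is due to CKD independently of age and sex, and an unadjusted contrast is acceptable as description. The objection does not remove the problem that section 6 describes the contrast in the language of assigned treatments.

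**Adjusted models are already planned, and an SAP may supply detail.** Covariate lists can be left to an SAP. But the protocol itself names the primary test, and an SAP that adjusted it would depart from the protocol. The point is a rule that is stated, not a detail that is missing.

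**The size is assumed.** This stands in full. A reader might infer that the groups are known to differ in age or sex, or that the error rate is known to be as high as 48%. The document says neither. A reader might also suspect that a pre-existing gap between the groups would be mistaken for a different response to iron. That would require the month-3 level to be the end point, which the protocol never states; objective 1 speaks of levels before and after treatment and of changes. Nor can it be claimed that adjusting for age and sex restores a 5% error rate: that is true only if all the confounding lies in those two variables.

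**Conclusion.** The point holds for what section 6 fixes. The primary comparison is labelled as if treatment had been assigned, the protocol is open to two readings of which groups are compared, and the unadjusted test supports description but not attribution to CKD or to iron route. This follows from the text and needs no assumption about the patients.

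The size of any bias is unknown. The rejection rates of 7.7% to 48% show only how sensitive the test would be to assumed shifts of 0.05 to 0.20 SD. They rest on a continuous end point, the CKD versus no-CKD reading, and 174 versus 196 patients analysed. If the primary end point is the percentage on which section 2.2 is sized, or if the contrast is oral versus intravenous, those SD-based figures do not apply, although the structural point does.

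**What to change.** In section 6:
1. State which two groups are compared (section B indicates CKD versus no CKD) and name the primary end point.
2. Make the primary comparison covariate-adjusted, with at least age and sex, using V1 and V2 data. If the end point is continuous and repeated, use the planned linear mixed model or a linear model. If it is the percentage behind section 2.2, use logistic regression. Whether to model change or the month-3 level adjusted for baseline is the sponsor's choice, to be fixed in advance.
3. Keep the unadjusted test as supportive.
4. Treat iron route as a sensitivity analysis only, because route may follow from CKD status and so is not clearly a confounder.
5. Replace the intention-to-treat wording with: *observational comparison of all enrolled patients, in their original group, regardless of later withdrawal or change of iron route*.

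The cost is a rewording of section 6, a little more analysis and some precision. Under the assumed gaps, age adjustment alone raises the detectable difference from 0.292 SD to between 0.301 and 0.326 SD, and the unfavourable combination above raises it to about 0.41 SD. Confounding by factors other than age and sex remains, and the report should say so.
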